	Indicated	Instrumental ADL	existing hospitalization indicated; disabling;			
			limiting self care			
	I	Metabolism and nutr	ition disorders	.		
Grade						
Adverse Event	1	2	3	4	5	

Confidential

Protocol No. CAAA601A22301

	a	a	a			
Anorexia	Loss of appetite without alteration in eating habits	Oral intake altered without significant weight loss or malnutrition; oral nutritional supplements indicated	Associated with significant weight loss or malnutrition (e.g., inadequate oral caloric and/or fluid intake); tube feeding or TPN indicated	Life-threatening consequences; urgent intervention indicated	Death	
Definition: A disorder ch	naracterized by a loss of	appetite.				
Tumor lysis syndrome	-	-	Present	Life-threatening consequences; urgent intervention indicated	Death	
Definition: A disorder characterized by metabolic abnormalities that result from a spontaneous or therapy-related cytolysis of tumor cells.						
Metabolism and nutrition disorders - Other, specify	Asymptomatic or mild symptoms; clinical or diagnostic observations only; intervention not indicated	Moderate; minimal, local or noninvasive intervention indicated; limiting age- appropriate instrumental ADL	Severe or medically significant but not immediately life- threatening; hospitalization or prolongation of existing hospitalization indicated; disabling; limiting self care ADL	Life-threatening consequences; urgent intervention indicated	Death	

Common Terminology Criteria for Adverse Events (CTCAE) v5.0 Publish Date: November 27, 2017

Introduction

The NCI Common Terminology Criteria for Adverse Events is a descriptive terminology which can be utilized for Adverse Event (AE) reporting. A grading (severity) scale is provided for each AE term.

SOC

System Organ Class (SOC), the highest level of the MedDRA¹ hierarchy, is identified by anatomical or physiological system, etiology, or purpose (e.g., SOC Investigations for laboratory test results). CTCAE terms are grouped by MedDRA Primary SOCs. Within each SOC, AEs are listed and accompanied by descriptions of severity (Grade).

CTCAE Terms

An Adverse Event (AE) is any unfavorable and unintended sign (including an abnormal laboratory finding), symptom, or disease temporally associated with the use of a medical treatment or procedure that may or may not be considered related to the medical treatment or procedure. An AE is a term that is a unique representation of a specific event used for medical documentation and scientific analyses. Each CTCAE v4.0 term is a MedDRA LLT (Lowest Level Term).

Grades

Grade refers to the severity of the AE. The CTCAE displays Grades 1 through 5 with unique clinical descriptions of severity for each AE based on this general guideline:

- Grade 1 Mild; asymptomatic or mild symptoms; clinical or diagnostic observations only; intervention not indicated.
- Grade 2 Moderate; minimal, local or noninvasive intervention indicated; limiting ageappropriate instrumental ADL*.
- Grade 3 Severe or medically significant but not immediately life-threatening; hospitalization or prolongation of
- hospitalization indicated; disabling; limiting self care ADL**. Grade 4 Life-threatening consequences; urgent
- intervention indicated. Grade 5 Death related to AE.
- A Semi-colon indicates 'or' within the description of the grade.

A single dash (-) indicates a Grade is not available. Not all Grades are appropriate for all AEs. Therefore, some AEs are listed with fewer than five options for Grade selection.

Grade 5

Grade 5 (Death) is not appropriate for some AEs and therefore is not an option.

Definitions

A brief Definition is provided to clarify the meaning of each AE term. A single dash (-) indicates a Definition is not available.

Navigational Notes

A Navigational Note is used to assist the reporter in choosing a correct AE. It may list other AEs that should be considered in addition to or in place of the AE in question. A single dash (-) indicates a Navigational Note has not been defined for the AE term.

Activities of Daily Living (ADL)

*Instrumental ADL refer to preparing meals, shopping for groceries or clothes, using the telephone, managing money, etc. **Self care ADL refer to bathing, dressing and undressing, feeding self, using the toilet, taking medications, and not bedridden.

Appendix 8 – Determination of LUTATHERA Administered Radioactivity

The total amount of radioactivity administered to the patient is determined by measuring the radioactivity present in the LUTATHERA (¹⁷⁷Lu-DOTA⁰-Tyr³-Octreotate, Infusion Solution) Vial before and after administration. The procedure is as follows:

A. Measurement of LUTATHERA Vial radioactivity before LUTATHERA administration:

- 1) remove the LUTATHERA Vial from the original package;
- 2) place the LUTATHERA Vial in the dose calibrator (activimeter) chamber;
- 3) select the Lu-177 setting on the dose calibrator;
- 4) press the "measure" button (or equivalent function button);
- 5) record the measured radioactivity, and the time of measurement in the appropriate electronic Case Report Form (eCRF);
- 6) remove the LUTATHERA Vial from the dose calibrator chamber;
- 7) return the LUTATHERA Vial to its original package or prepare the Vial for patient administration.

B. Measurement of LUTATHERA vial radioactivity *after* LUTATHERA administration:

- remove needles and tubing attached to the LUTATHERA Vial (NB: The investigator must confirm that there is no significant residual radioactivity remaining in delivery needles and tubing after administration (< 0.1% of original Total Radioactivity in LUTATHERA Vial);
- 2) if the dose calibrator is in a different location, place the LUTATHERA Vial in the original package so that the material can be moved safely otherwise go to step 4;
- 3) remove the LUTATHERA Vial from the original package;
- 4) place the LUTATHERA Vial in the dose calibrator chamber;
- 5) select the Lu-177 setting on the dose calibrator;
- 6) press the "measure" button (or equivalent function button);
- 7) record the measured radioactivity, and the time of measurement in the appropriate eCRF;
- 8) remove the LUTATHERA Vial from the dose calibrator chamber and dispose according to national and local regulations for disposal of radioactive waste;

C. Calculation of Total Administered and Residual Radioactivity:

- 1) Total Administered Radioactivity
 - = (amount of radioactivity in LUTATHERA Vial before administration minus amount of radioactivity in LUTATHERA Vial after administration) times vial geometry correction factor

= (A.5 – B.7) x Correction Factor;

2) Residual Radioactivity = amount of radioactivity remaining in LUTATHERA Vial after administration times vial geometry correction factor

= B.7 x Correction Factor;

3) record Total Administered Radioactivity and Residual Radioactivity in the appropriate sections of the patient's eCRF.

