6.1.1.1 Lutathera arm

6.1.1.1.1 Investigational Drug Product: Lutathera® (¹⁷⁷Lu-Dotatate)

Lutathera is a sterile radiopharmaceutical supplied as a ready-to-use solution for infusion containing ¹⁷⁷Lu-DOTA⁰-Tyr³-Octreotate as Drug Substance with a volumetric activity of 370 MBq/mL at reference date and time (calibration time (tc)).

On the day of Lutathera treatment, an intravenous bolus of anti-emetic is given. For renal protection, a sterile amino acids solution is infused 30 minutes before the start of Lutathera, and continues for a total of 4 h. See further details in Section 6.6.

Lutathera is a radiopharmaceutical solution for infusion supplied as a ready-to-use product. The only Quality Control (QC) tests that must be performed at the clinical site are; 1) confirm correct product certificate; 2) determine total radioactivity; 3) confirm visual appearance. Since Lutathera is manufactured in centralized GMP facilities, the majority of required QC tests are performed before product shipment. A batch release certificate of the product will be sent to the investigational centres. This batch release certificate is provided by the Qualified Person (QP) of the manufacturing site to ensure that the product is suitable for administration and that it meets the specifications indicated in the product leaflet.

Manufacturing site prepares single doses calibrated within the range of 7.4 GBq \pm 10 % (200 mCi) between t0+6h and t0+52h after the end of production. Certificate of release reports both the exact activity provided and the time when this activity is reached. The total amount of radioactivity per single dose vial is 7,400 MBq at the date and time of infusion. Given the fixed volumetric activity of 370 MBq/ml at the date and time of calibration, the volume of the solution is adjusted between 20.5 ml and 25.0 ml in order to provide the required amount of radioactivity at the date and time of infusion.

The composition of the drug product is listed in Table 6-2 below.

Component	Content (Unit and/or percentage)		Function	Quality standards
	V= mL (min volume)	V= mL (max volume)		
Drug Substance: ¹⁷⁷ Lu-DOTA ⁰ -Tyr ³ - Octreotate (volumetric activity)	MBq/mL (EoP)	± % at Tc	Drug Substance	-
Activity at Injection time	GBq ±	%	-	-
¹⁷⁶⁺¹⁷⁷ Lu-DOTA ⁰ -Tyr ³ - Octreotate ²	μg	μg	-	NA ¹
DOTA-Tyr ³ -Octreotate	μg	μg	Chemical precursor	-
Excipients*				
Acetic acid	mg	mg	pH adjuster	In-house
Sodium acetate	mg	mg	pH adjuster	In-house

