The surface dose rates and the accumulated dose depend on many factors. Measurements on the location and during work are critical and should be practiced for more precise and instructive determination of overall radiation dose to the staff. Healthcare personnel are advised to limit the time of close contact with patients injected with Lutathera. The use of television monitor systems to monitor the patients is recommended. Given the half life of 177Lu it is specially recommended to avoid internal contamination. It is necessary to use protective high quality (latex/nitrile) gloves to avoid direct contact with the radiopharmaceutical (vial/syringe). For minimizing radiation exposure, always use the principles of time, distance and shielding (reducing the manipulation of the vial and using the material already supplied par the manufacturer).

This preparation is likely to result in a relatively high radiation dose to most patients. The administration of 7,400 MBq may result in significant environmental hazard.

This may be of concern to the immediate family of those individuals undergoing treatment or the general public depending on the level of activity administered, hence radioprotection rules should be followed. Suitable precautions in accordance with national regulations should be taken concerning the activity eliminated by the patients in order to avoid any contaminations.

Any unused medicinal product or waste material should be disposed according to local requirements.

INSTRUCTIONS FOR THE USE OF Lutathera (7400 MBq)

Lutathera is for single use only.

The solution should be visually inspected for damage and contamination before use, and only clear solutions free of visible particles should be used. The visual inspection of the solution should be performed under a shielded screen for radioprotection purposes. The vial must not be opened.

If at any time in the preparation of this medicinal product the integrity of this vial is compromised, it should not be used.

The amount of radioactivity in the vial must be measured prior to infusion using a suitable radioactivity calibration system in order to confirm that the actual amount of radioactivity to be administered is equal to the planned amount at the infusion time.

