2.4.1.2 Cumulative dose

Cumulative dose of a study treatment is defined as the total dose given during the study treatment exposure and will be summarized for each of the study treatment components, separately for randomized period, cross-over period, and re-treatment period, except that the cumulative dose for Octreotide in the re-treatment period will not be summarized due to very limited cases (Octreotide is optional in the re-treatment period).

The **planned cumulative dose** for a study treatment component refers to the total planned dose as per the protocol up to the last date of that study treatment component administration.

The planned cumulative dose is not summarized/listed. It is used for relative dose intensity calculations.

The **actual cumulative dose** refers to the total actual dose administered, over the duration for which the subject is on the study treatment as documented in the Dose Administration eCRF.

For patients who did not take any drug the cumulative dose is by definition equal to zero.

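### Appendix 8 computes administered Lutathera activity from two vial readings at different times without referring either to infusion time, so decay biases the recorded dose upward

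*Protocol*

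**What the plan says.** Protocol Section 6.6 names Appendix 8 as the procedure for determining administered radioactivity. Step A measures the vial before administration and step B measures it afterwards. Step C.1 gives the administered total as ("amount of radioactivity in LUTATHERA Vial before administration minus amount of radioactivity in LUTATHERA Vial after administration) times vial geometry correction factor"), written as (A.5 - B.7) x Correction Factor. Step C.2 gives the residual as B.7 x Correction Factor. The only correction is for vial geometry.

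At A.5, and in almost the same words at B.7, the site is told to "record the measured radioactivity, and the time of measurement in the appropriate electronic Case Report Form (eCRF"), so both clock times are captured. Appendix 6, under quality control, also has infusion start and stop times recorded. After the first reading, step A.7 tells the site to "return the LUTATHERA Vial to its original package or prepare the Vial for patient administration". No interval to infusion is given.

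Elsewhere the dose is tied to infusion time. Section 6.1.1.1.1 states: "The total amount of radioactivity per single dose vial is 7,400 MBq at the date and time of infusion". Appendix 6 requires a measurement before infusion to confirm that the "actual amount of radioactivity to be administered is equal to the planned amount at the infusion time".

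Section 6.5.1 allows each dose to deviate by 10% either way. In SAP 2.4.1.2 the actual cumulative dose "refers to the total actual dose administered", taken from the Dose Administration eCRF. SAP 2.4.1.3 then derives dose intensity, and relative dose intensity against a planned 0.925 GBq/week.

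**The concern.** The first reading is taken while the vial holds more activity than it will at infusion. The residual is read when it holds less than it did at infusion. Subtracting one from the other therefore does not give activity at infusion, which is how the protocol defines the dose. Both errors have the same sign, so averaging over doses or patients does not remove them. The times needed to correct them are collected, but step C does not use them.

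At stake is the accuracy of the recorded Lutathera dose and of the exposure tables built on it. Section 6.1.1.1.1 itself treats decay as large enough to change the fill volume from vial to vial.

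**Working it through.** **Inputs**
- Lu-177 half-life: 6.71 days = 161.04 h (Appendix 4, Table 1; the table text is broken in the copy read, so it is checked below). Decay constant λ = ln 2 / 161.04 = 0.004304 per h.
- "fixed volumetric activity of 370 MBq/ml at the date and time of calibration", and 7,400 MBq per vial at infusion (Section 6.1.1.1.1).
- Calibration window "between t0+6h and t0+52h after the end of production", with fill volume 20.5 to 25.0 mL (same section).
- Tolerance per dose: ±10% (Section 6.5.1), so the upper limit is 7.4 x 1.10 = 8.14 GBq.

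**Reproducing the plan's own decay figure.** Volume needed = (7,400 / 370) x exp(λh) = 20 x exp(λh).
- h = 6: 20 x 1.0262 = 20.52 mL (stated 20.5).
- h = 52: 20 x 1.2508 = 25.02 mL (stated 25.0).

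The half-life is confirmed, and the protocol corrects for decay when filling the vial.

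**Bias in step C.** Let A be read at t1, infusion take place at t2, and B be read at t3, with the geometry factor cancelling.
- Recorded = A - B.
- True at infusion = A exp(-λ(t2 - t1)) - B exp(λ(t3 - t2)).
- Recorded - true = A[1 - exp(-λ(t2 - t1))] + B[exp(λ(t3 - t2)) - 1].

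Neither term can be negative, so decay acts only upward.

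**Size, with negligible residual.** Excess relative to true activity = exp(λ x gap) - 1.

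| Gap from first reading to infusion | Excess |
|---|---|
| 0.5 h | 0.22% |
| 1 h | 0.43% |
| 4 h | 1.74% |
| 8 h | 3.5% |
| 12 h | 5.3% |
| 24 h (assumed) | 10.88% |

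The excess passes 10% at ln(1.1) / λ = 22.1 h.

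**Residual term.** With 5% of the activity left in the vial, read 1 h after infusion, and no gap before infusion, the excess is 0.05 x (1 - exp(-λ)) / 0.95 = 0.02%. The pre-infusion reading is what matters.

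**One-day illustration.** A vial holding 7.4 GBq at infusion and read 24 h earlier would be recorded as 7.4 x 1.1088 = 8.21 GBq, above 8.14 GBq.

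**Effect on exposure summaries.** Take four full doses at exact 8-week intervals: 29.6 GBq over 3 x 56 + 55 + 1 = 224 days = 32 weeks. Then 29.6 / 32 = 0.925 GBq/week and relative dose intensity is 100%. With a 4 h gap at every dose, cumulative dose becomes 29.6 x 1.0174 = 30.1 GBq and relative dose intensity 101.7%. With a 1 h gap it is 100.4%.

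**Scale within the procedure.** Step B.1 requires activity left in needles and tubing to be below 0.1% of the original. Decay reaches 0.1% in 0.001 / 0.004304 = 0.23 h, about 14 minutes.

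**The case against.** The strongest reply is that practice probably keeps the gap short. The Appendix 6 measurement serves to confirm activity at infusion time, which points to a reading close to infusion or referred to it. Returning the vial to its package in step A.7 need not mean storage: the package is the lead shielding, and step B.2 uses it simply to move the vial safely. With readings 1 to 4 h before infusion the excess is 0.4% to 1.7%, well inside the tolerance. The pharmacy manual and the eCRF calculations are not among the documents and could contain the correction. Section 6.5.1 does not say that the ±10% check uses the Appendix 8 result, and SAP 2.4.1.4 takes dose reductions from a separate eCRF field.

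All of that stands, and it limits the size of the problem. It does not remove the gap in the stated method: no interval is set, no decay step is given, and step C.3 sends the uncorrected result to the eCRF.

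A reader might also infer that a genuine under-dose could be recorded as a full dose. The documents do not support this. Section 6.1.1.1.1 has the vial filled to hold 7,400 MBq at infusion, with a release certificate stating the activity and when it is reached. Such a vial read a day early would look like an over-dose. A hidden shortfall would need an under-filled vial, an early reading and a failed Appendix 6 check together.

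**Conclusion.** The point holds as a minor defect in the stated calculation. As written, step C gives a value that decay biases upward, by about 0.4% at 1 h, 1.7% at 4 h and 5.3% at 12 h. These figures rest on the 6.71-day half-life and a small residual. The actual gaps are not given in the documents.

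The 10.9% figure depends on the assumed 24 h gap. It should not be read as the expected error, because no section describes a day-before reading. It is not a ceiling either, because the only outer time limit is the 72 h shelf life in Appendix 6.

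The upward direction applies to decay alone; calibrator or geometry error could go either way. The effect is confined to recorded dose and to descriptive summaries of cumulative dose, dose intensity and relative dose intensity for Lutathera. PFS, the key secondary endpoints and the sample size are untouched.

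**What to change.** In Appendix 8, C.1 and C.2, refer both readings to infusion start with one stated Lu-177 half-life T:
- pre-infusion reading: A.5 x 2^(-(t2 - t1)/T)
- residual reading: B.7 x 2^((t3 - t2)/T)

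The recorded measurement times and infusion start time supply t1, t2 and t3. Choosing infusion start rather than stop changes the result by only about 0.2% over a 30-minute infusion.

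In SAP 2.4.1.2, first establish whether the eCRF or the pharmacy manual already applies this correction. If so, say so in Appendix 8. If not, re-derive administered activity from the recorded readings and times before computing cumulative dose, dose intensity and relative dose intensity. Recruitment was complete when protocol version 2.0 was issued, so the SAP step does most of the work.

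The cost is one formula change and one programming step on data already collected. Recorded doses and relative dose intensity will fall slightly. If the recorded gaps prove short, the re-derivation documents that the bias was negligible.

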18-Nov-2022	Prior to DB lock	Incorporating amendments 1 and 2 of protocol	
Update roles and participants for signatures
 
Addition of reference to Amendments 1 and 2 of protocol
 
Addition of reference to optional re-treatment phase
 
Update study design figure
 
Minor editorial updates for the endpoints
 
Addition of re-treatment exploratory endpoints
 
Addition/update of general definitions to account for the addition of re-treatment and to clarify some definitions
 
Update of Table 2.2.1
 
Addition of appropriate summaries and listings for patients who crossover or receive re-treatment therapy separately
 
Addition of appropriate summaries and listings for the extension and re-treatment phases
 
Addition of appropriate summaries and listings for the extension and re-treatment phases
 
Addition of more details to improve clarity on estimation of PFS at the primary analysis
 
Addition of more details on censoring and progression rules for PFS
 
Updated Table 2.5-1
 
Addition of supportive analyses to support estimand analysis
 
Highlighting that COVID-19 sensitivity analysis will be discussed in SAP
 
Addition of the 24 week requirement for SD
 
Addition of exploratory PFS, ORR, DCR, DoR, PFS2 and OS analysis in re-treatment Lutathera patients sub-section
	
Signature Page
 
1. Introduction
 
1.1 Study Design
 
1.2 Study objectives and endpoints
 
2.1.1 General definitions updates
 
2.2 Analysis Sets
 
2.3 Patient disposition, demographics and other baseline characteristics
 
2.4.1 Study treatment / compliance
 
2.4.2 Prior, concomitant and post therapies
 
2.5.1 Primary endpoint
 
2.5.3 Handling of missing values/censoring/discontinuation
 
2.5.6 Supportive analyses
 
2.7.1 Other secondary and exploratory endpoints

Date	Time point	Reason for update	Outcome for update	Section and title impacted (Current)
			Moved Table 2.7-1 to Section 2.7.3	
			Removed censoring language for DOR since that is mentioned in 2.7.1	2.7.2 Statistical hypothesis, model, and method of analysis
			Highlighted that all efficacy analysis for re-treatment phase is descriptive	
			Added PFS2 censoring rules	2.7.3 Handling of missing values/censoring/discontinuation
			Added statement on OS censoring	
			Highlighted throughout section that safety analyses will be conducted for the on-treatment period, crossover period, and re-treatment period separately	2.8 Safety analyses
			Highlighted that for AE summaries, SOCs will be collected alphabetically.	2.8.1 Adverse events (AEs)
			Stated that all AE groupings for a clinical program are stored in CRS	2.8.1.2 Adverse events of special interest/ grouping of AEs
			Added details about potential Hy's law events	2.8.3 Laboratory data
			Highlighted that if an ECG is conducted, but data is not available in triplicate, the average of the ECG parameters at that assessment should be used in the analysis.	2.8.4.1 ECG and cardiac imaging data
			Added analyses to support dosimetry collection in Germany	
			Moved duration of follow-up analysis to this section	2.10 Dosimetry analysis
			Separated follow-up time for PFS and OS For PFS follow-up, highlighted that this is for 1 st central progression	2.12 Duration of follow-up
			Replaced dose with treatment throughout section	5.1.1 Study treatment
			Event end date only applicable for AE and CM datasets in Table 5.1-1	5.1.2 AE, ConMeds and safety assessment date imputation
			Clarified Table 5.1-2 to capture end date of final treatment on trial	
			Imputation used to determine TEAEs	
			Removed project specific ranges language	5.3 Laboratory parameters derivations
			Added information on missing scan capturing	5.5 Determination of missing adequate assessments
22-Aug-2023	Prior to DB lock	To align on more details of analysis rules before DBL	
 Added 'unconfirmed' for CR and PR. Removed PD, disposition by center summary Clarified baseline for cross-over/re-treatment. Updated terms for study phase 	1.3.2 Secondary estimand #1 2.1 Data analysis general information 2.1.1.8 Baseline 2.1.1.9 Definition of study phases

Date	Time	Reason for update point	Outcome for update	Section and title impacted (Current)
			
Updated section title from 'On-treatment assessment/event' to 'Definition of treatment periods used in analyses'; updated definitions for different treatment periods; added definition for between treatment period; clarified scope of cross-over/re-treatment analyses at the time of primary PFS analysis.Added analysis window table for PRO data; removed wordings that are not applicable for this study; updated source for last contact date.Updated subgroups based on clinical input.Added Table 2-3 for grouping of primary sites of cancer; removed baseline characteristics summary for cross-over/re-treatment at the time of primary PFS analysis; removed major protocol deviation leading to exclusion from analysis, which is not applicable for this study.Adjusted exposure summaries for study treatment based on actual data in this study; added clarification for PDI of Octreotide LARAdjusted summaries for prior anti-cancer therapy; also removed redundant wordings that are not applicable to this study or for the primary PFS analysis.Removed censoring rule for supplementary analysis from Table 2.5-1, which is already covered later.Removed repeated paragraph; shifted PFS analysis based on local assessment to 2.5.6 supplementary analysis; adjusted variables to be considered in stratified multivariate Cox model; removed unstratified multivariate Cox model from the sensitivity analyses.Clarified detailed PFS analyses for subgroups; fixed derivation logic for PFS censoring reasons; added rules for waterfall plot.	2.1.1.10 Definition of treatment periods used in analyses
				2.1.1.11 Windows for multiple assessments.
